TSH	Thyroid Stimulating Hormone
VWF	Von Willebrand Factor
Wbp	Personal Data Protection Act (in Dutch: Wet Bescherming Persoonsgegevens)
WES	Whole Exome Sequencing
WMO	Medical Research Involving Human Subjects Act (in Dutch: Wet Medisch-wetenschappelijk Onderzoek met Mensen)

SUMMARY

Rationale: Rare bleeding disorders (deficiency of fibrinogen, factor II, V, V&VIII, VII, X, XI, XIII, α 2-antiplasmin or plasminogen activator inhibitor 1) are not well defined with respect to their clinical phenotype, laboratory phenotype en genotype. At present, little is known about their clinical presentation, bleeding scores, bleeding episodes, health-related quality of life, laboratory parameters, genetics and current treatment. There are large differences in bleeding tendency and weak correlations with the level of factor deficiencies. Therefore, it is essential to perform thorough research in patients with rare bleeding disorders and perform laboratory and genetic tests, to seek explanations for the variety in clinical phenotype.

Objective: The purpose of the RBiN study is to describe the epidemiology, bleeding tendency, laboratory parameters, quality of life and genetics of all known patients in the Netherlands with rare bleeding disorders. In addition, the study aims to examine the relationship between clinical phenotype, laboratory phenotype and genotype.

Study design: cross-sectional multicenter observational study.

Study population: all patients registered in Dutch Haemophilia Treatment Centers with known disorders of the coagulation factors fibrinogen, factor II, V, V & VIII, VII, X, XI, XIII, α 2-antiplasmin and plasminogen activator inhibitor type 1, aged 1 years and older.

Main study parameters/endpoints:

Description of the clinical phenotype, laboratory phenotype, genotype and quality of life.

Nature and extent of the burden and risks associated with participation, benefit and group relatedness: participating patients will be invited for one visit to their treatment center in order to draw blood, take a saliva sample and perform questionnaires. This will take approximately 40 to 120 minutes. Since the population of patients with RBDs is very small it is important to include all patients, also minors (children <18 years), in the study (around one third of known patients are minors). Therefore, this study may be regarded as group-related. The risk associated with participation is negligible.

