3. OBJECTIVES

Our primary objectives are to:

- Describe the epidemiology, clinical presentation, bleeding score, bleeding episodes, quality of life, laboratory parameters, genetics and treatment of *homozygous* and known *heterozygous* individuals (of all ages) with rare bleeding disorders (disorders of fibrinogen, FII, FV, FV & VIII, FVII, FX, FXI, FXIII, alpha-2-antiplasmin and PAI-1 deficiency) in the Netherlands;
- Examine the relationship between the clinical and laboratory presentation (clinical and laboratory phenotype), and between phenotypes and genetics (genotype);
- Examine the relationship between quality of life, phenotype and genotype;
- ~~Validate the established factor activity levels for patients to remain without symptoms.~~

Our secondary objectives are to:

- Validate the established factor activity levels for patients to remain without symptoms.
- Compare the clinical presentation, bleeding score, quality of life and laboratory parameters of individuals with a rare bleeding disorder (disorders of fibrinogen, FII, FV, FV & VIII, FVII, FX, FXI, FXIII, alpha-2-antiplasmin and PAI-1 deficiency) to those of individuals with haemophilia A or B in cooperation with the HIN-6 investigators
- Establish a firm base for a future Dutch registry for *homozygous* and known *heterozygous* individuals with rare bleeding disorders
 - To develop a standard set of patient-reported, clinical and administrative data to be collected on a regular basis
- Liaise with the pro-RBDD study, a similar study in Italy, to work towards a pan-European study linking phenotype to genotype in individuals with rare bleeding disorders
- To assess if the NHA can distinguish mild clinical phenotypes in patients with similar factor activity levels
- To evaluate the usefulness of saliva coagulation biomarker tests in the management of patients with a rare bleeding disorder
- To examine whether age-dependent laboratory changes in factor concentrations and fibrinolysis occur in individuals with rare bleeding disorders and if so, whether they influence clinical phenotype
- To evaluate if patients with rare bleeding disorders are protected from arterial thrombosis

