Deficiency	Estimated prevalence homozygosity in general population as described in the literature [1, 2]	Estimated prevalence homozygosity in the Dutch general population	Patients known at present in the Netherlands (homozygous/heterozygous/unknown)
Fibrinogen	1:1 million	17	28
II	1:2 million	9	9
V	1:1 million	17	22
V & VIII	1:1-2 million	9-17	4
VII	1:500,000	34	92
X	1:1 million	17	10
XI	1:1 million	17	88
XIII	1:1-2 million	9-17	16
PAI-1	Unknown	Unknown	39
Alpha-2-antiplasmin	Unknown	Unknown	29
	Total	129-145	337

Abbreviations: CI: confidence interval

\$ Based on a population figure of 17,024,133 (www.cbs.nl/nl-nl/visualisaties/bevolkingsteller)

* Based on a quick inventory of participating sites, which are all sites in the Netherlands licensed to treat rare bleeding disorders. Homozygosity or heterozygosity largely unknown

Willingness of patients to participate

We expect that a high proportion of patients with rare bleeding disorders are willing to participate in RBiN. Patients are aware of the rarity of their disorder and the lack of research. The Netherlands Hemophilia Society (Nederlandse Vereniging van Hemofilie Patiënten, NVHP) is a co-initiator of RBiN and a patient representative takes seat in the steering committee. Based on the response rate of the HiN studies we expect a (similar) response rate of 70% [51].

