6.5. Follow-up of subjects withdrawn from treatment

Not applicable as this study has no follow-up.

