7.1. Primary objectives

- *Describe the epidemiology, clinical presentation, bleeding score, bleeding episodes, quality of life, laboratory parameters, genetics and treatment of homozygous and known heterozygous individuals (of all ages) with rare bleeding disorders (disorders of fibrinogen, FII, FV, FV & VIII, FVII, FX, FXI, FXIII and alpha-2-antiplasmin and PAI-1 deficiency) in the Netherlands;*

We will use descriptive statistics using means, SD and medians. Interquartile ranges will be used when appropriate. Prevalence will be reported with 95% confidence intervals.

- *Examine the relationship between clinical and laboratory presentation (clinical and laboratory phenotype), and between phenotypes and genetics (genotype);*

Descriptive statistics will be used. Regression analysis will be used to determine the association between coagulation factor activity level (dependent variable) and clinical

bleeding severity as a continuous variable (independent variable), with adjustment for age at data collection, sex, etcetera.

- *Examine the relationship between quality of life, phenotype and genotype;*
Descriptive statistics will be used. Regression analysis will be used to determine the association between quality of life (dependent variable) and clinical bleeding severity or coagulation factor activity level as a continuous variable (independent variable), with adjustment for age at data collection, sex, etcetera.
- *Validate the established factor activity levels for patients to remain without symptoms.*
Descriptive statistics will be used.

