7.2. Secondary objectives

- *Compare the clinical presentation, bleeding score, quality of life and laboratory parameters of individuals with a rare bleeding disorder (disorders of fibrinogen, FII, FV, FV & VIII, FVII, FX, FXI, FXIII and alpha-2-antiplasmin and PAI-1 deficiency) to those of individuals with haemophilia A or B (HiN study data will be shared)*
Descriptive statistics will be used. Group differences will be determined using the statistics as described in Statistical Analysis above.
- *Establish a firm base for a future Dutch registry for homozygous and known heterozygous individuals with rare bleeding disorders (disorders of fibrinogen, FII, FV, FV & FVIII, FVII, FX, FXI, d FXIII and alpha-2-antiplasmin and PAI-1 deficiency):*
 - *To develop a standard set of patient-reported, clinical and administrative data to be collected on a regular basis*

No statistics are involved in this objective.

- *Liaise with the pro-RBDD study, a similar study in Italy, to work towards a pan-European study linking phenotype to genotype in individuals with rare bleeding disorders*
No statistics are involved in this objective.
- *To assess if the NHA can distinguish mild clinical phenotypes in patients with similar factor activity levels*
We will calculate diagnostic accuracy comparing NHA to ISTH BAT.
- *To evaluate the usefulness of saliva coagulation biomarker tests in the management of patients with a rare bleeding disorder*
Descriptive statistics will be used. Regression analysis will be used to determine the association between saliva biomarker tests (dependent variable) and coagulation factor activity level as a continuous variable (independent variable), with adjustment for age at data collection, sex, etcetera.

- *To evaluate the use of WES in explaining differences in bleeding tendency.*
Descriptive statistics will be used.
- *To examine whether age-dependent laboratory changes in factor concentrations and fibrinolysis occur individuals with rare bleeding disorders? And if so, do they influence clinical phenotype?*
Descriptive statistics will be used. Regression analysis will be used to determine the association between age (dependent variable) and coagulation factor activity level as a continuous variable (independent variable), with adjustment for age at data collection, sex, etcetera.
- *To evaluate if patients with rare bleeding disorders are protected from arterial thrombosis*

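### The ageing regression in section 7.2 has age as both outcome and covariate, so it cannot show or exclude an age effect

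*Combined protocol and SAP*

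**What the plan says.** Section 3 lists as a secondary objective to examine "whether age-dependent laboratory changes in factor concentrations and fibrinolysis occur in individuals with rare bleeding disorders" and, if they do, whether they affect clinical phenotype. Section 7.2 gives the analysis: descriptive statistics, with no detail, and one regression, of the "association between age (dependent variable) and coagulation factor activity level as a continuous variable (independent variable), with adjustment for age at data collection", sex and further covariates that are not named.

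Three other places bear on how this is read:

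- **Design.** Section 4 calls the study cross-sectional. The Summary says that "participating patients will be invited for one visit to their treatment center", and section 6.5 reads "Not applicable as this study has no follow-up".
- **Measurements.** Table 4 (section 6.1) lists coagulation factor assays and five fibrinolysis markers (PAI-1, TPA, plasminogen, alpha-2-antiplasmin, TAFI) on study blood. It also takes a baseline factor activity level from patient records.
- **Nearest other model.** Section 7.1 has a regression for the "association between coagulation factor activity level (dependent variable) and clinical" bleeding severity, adjusted for age and sex. It serves a primary objective and is not assigned to the ageing question.

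**The concern.** The objective asks how laboratory values change with age. A regression that explains age by age leaves nothing for factor level to explain, so its output cannot depend on whether an age effect exists. If the rule is followed, the only model planned for this objective yields no estimate, interval or test. The analyst must then choose a replacement with the data in hand. Section 7 treats the study as exploratory and makes no multiplicity correction, so nothing else in the plan constrains that choice.

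There are two related gaps. The regression names only coagulation factor activity, although the objective also covers fibrinolysis; TPA, plasminogen and TAFI fall outside that term. The second half of the objective, influence on phenotype, has no model of its own.

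**Working it through.** The plan states no sample size, power or effect size for this objective, so there is no figure of its own to reproduce.

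**1. The model as written.** Least squares minimises

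Σ(ageᵢ − b₀ − b₁·factorᵢ − b₂·ageᵢ − b₃·sexᵢ)².

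Setting b₂ = 1 and b₀ = b₁ = b₃ = 0 makes every term zero, and no smaller sum is possible. If the columns are not collinear, this solution is unique. Hence the factor coefficient is 0, the age coefficient is 1 and R-squared is 1. The residual sum of squares is 0, so the standard error is 0 and the t statistic is 0/0. Any p-value that software prints is rounding noise.

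**2. Which fault causes this.** Drop age from the covariates. Then age on factor + sex and factor on age + sex have the same test statistic,

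t = r·√(n − 3) / √(1 − r²),

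where r is the partial correlation of age and factor given sex. Reversing the roles therefore leaves the p-value unchanged. The age covariate causes the degeneracy.

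**3. Simulation check.** Inputs: 92 known factor VII patients (Table 3) and an expected 70% response (section 5.1) give 92 × 0.70 = 64.4, so n = 64. Assumed, not in the documents: age uniform from 1 to 85, factor SD about 15, and the true correlations below. There were 1,000 data sets per row.

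| True correlation | As written: largest absolute factor coefficient | As written: R-squared | p < 0.05, age on factor + sex | p < 0.05, factor on age + sex |
|---|---|---|---|---|
| 0 | 2.0e-15 | 1.000 | 0.063 | 0.063 |
| 0.2 | 1.5e-15 | 1.000 | 0.332 | 0.332 |
| 0.3 | 1.7e-15 | 1.000 | 0.664 | 0.664 |
| 0.5 | 1.5e-15 | 1.000 | 0.990 | 0.990 |

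The model as written gives the same answer in every row. Without the age covariate the two directions agree; their p-values differ by at most 8e-14.

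**4. Why direction still matters for the estimate.** In one simulated data set (n = 64, true slope 0.2% activity per year, residual SD 10), factor on age gave 0.15% per year (95% CI 0.05 to 0.24). Age on factor gave 0.94 years per 1% activity. Inverting the second gives 1/0.94 = 1.06% per year, not 0.15. The reversed model therefore does not supply the change per year that the objective asks about.

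**5. What a corrected model could support, by disorder.** Expected n is the Table 3 count × 0.70, rounded. Residual df with intercept, age and sex is n − 3. The approximate 95% half-width for the change per 10 years is

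10 · t(0.975, n − 3) · SD / (24.2·√(n − 1)),

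with assumed residual SD 8 to 15 (% activity) and age SD 24.2 (uniform 1 to 85).

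| Disorder | Expected n | Residual df | Half-width, % activity per 10 years |
|---|---|---|---|
| FVII | 64 | 61 | 0.8 to 1.6 |
| FX | 7 | 4 | 3.7 to 7.0 |
| FII | 6 | 3 | 4.7 to 8.8 |
| FV & VIII | 3 | 0 | none (saturated) |

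For FVII at SD 8: 10 × 2.00 × 8 / (24.2 × 7.94) = 0.83. FXI is similar in size to FVII (n = 62, df 59). The other expected sizes are PAI-1 27, fibrinogen 20, alpha-2-antiplasmin 20, FV 15 and FXIII 11.

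**The case against.** **It is a drafting slip.** The same adjustment phrase appears in all four regressions of sections 7.1 and 7.2, so it was probably carried over. Any analyst would notice an R-squared of 1, and deleting one covariate restores a valid test. This is fair and limits the harm. It does not say what replaces the model: outcome, fibrinolysis markers, pooling and the unnamed covariates would all remain open.

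**The objective is secondary and exploratory, and descriptive statistics are also planned.** These could show a crude age pattern. No age-specific summary, interval or test is named, however. The Wilcoxon comparison of age and factor levels later in section 7.2 belongs to the arterial thrombosis objective.

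**Another age may have been meant.** Table 4 takes a baseline factor level from records, so an age at that measurement could exist, and the model would then not be exactly degenerate. The plan neither defines nor uses such an age. If it was intended, the text still needs correcting, because a model adjusted for current age is not a plain test of change with age. The point does show that a corrected model must say which factor level it uses.

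**The illustration rests on assumptions.** This stands, but the central result is algebra and needs none of them. Uniform ages from 1 to 85 put 17/84 = 20% under 18, whereas the Summary and section 8.4 say about one third of known patients are minors. A mix of one third uniform 1–18 and two thirds uniform 18–85 has SD about 25.5 instead of 24.2, so the half-widths would be about 5% narrower.

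**The fibrinolysis and phenotype gaps are separate.** Agreed: they do not follow from the circular model. They concern the same objective and can be settled in the same edit.

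**Conclusion.** The concern holds. As written, the only regression assigned to the ageing objective returns 1 for age, 0 for factor level and R-squared of 1 regardless of the data. This rests on age and age at data collection being the same variable, which is the natural reading of a one-visit study with no second age defined. The adjustment for age is the fault that destroys the analysis. Having age as the outcome is a lesser fault: it leaves the test intact once the covariate is removed, but gives a slope in years per unit of factor.

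The consequence is limited to one secondary, exploratory objective. The failure would be visible at once, so the realistic cost is a post hoc replacement model. It should be corrected before analysis because the correction is cheap and nothing else in the plan supplies a test or interval for age.

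**What to change.** Replace the regression sentence for this objective in section 7.2 with wording such as: *The activity level of the deficient factor, and each fibrinolysis marker, measured in the study-visit sample, will be the dependent variable, with age at data collection (linear) as the exposure, adjusted for sex.* Then:

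- Remove age from the adjustment list for this objective, and name the covariates in place of the open-ended list. Zygosity (where known) and prophylactic treatment both bear on factor level, so state how each is handled.
- Fit by disorder where numbers allow, for example FVII and FXI. Report very small groups such as FV & VIII, FII and FX descriptively, for instance as a plot of level against age.
- For the phenotype half, add a model in the larger groups with bleeding score or grade as the outcome and age and factor level as predictors, adjusted for sex.

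The cost is SAP wording only, since sections 6.1 and 6.2 already provide for collecting these variables. The downside is a little more exploratory analysis and no model estimate in the smallest disorders.

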8. ETHICAL CONSIDERATIONS

8.1. Regulation statement

This study will be conducted in accordance to the principles of the Declaration of Helsinki, ICH guidelines on Good Clinical Practice (GCP) and in accordance with the Medical Research Involving Human Subjects Act (WMO). The local investigator is responsible for ensuring that the study will be conducted in accordance with the protocol, ethical principles, ICH-GCP guidelines and the WMO.

8.2. Recruitment and consent

Subjects will be informed about the study by their treating physician. A minimum of one week will be allowed to consider their decision to participate after giving informed consent. The patient information letter and informed consent (in Dutch) are attached as separate documents.

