4. STUDY DESIGN

RBiN is a cross-sectional observational study. All participants will be asked to fill out questionnaires, will be interviewed, and asked to provide blood and saliva samples. The blood samples will be used for analyses and to set up a biobank.

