5.2. Inclusion criteria

In order to be eligible to participate in this study, a subject must meet all of the following criteria:

- Established homozygous or known heterozygous rare bleeding disorder due to deficiency or dysfunction of fibrin, FII, FV, FV & FVIII, FVII, FX, FXI, FXIII, alpha-2-antiplasmin and PAI-1 ;
- Age 1 year and older;

- For patients ≥ 16 years old; written informed consent.
- For patients 12-16 years old; written informed consent from both the patient and their parents/legal guardian(s).
- For patients <12 years old; written informed consent from their parents/legal guardian(s).

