6. METHODS

6.1. Study procedures

Patients will be approached by their own treating physician. Data will be collected through questionnaires, a clinical interview, a blood and saliva sample obtained from each participant, and thorough review of electronic patient records. An overview of study procedures is given in Table 4. All procedures are study related. In case a physician visit with the treating physician is already planned, or in case a venepuncture for regular diagnostics or treatment is already planned, this can be combined with the study procedures to prevent an extra visit.

Table 4 Overview of study procedures for each adult subject

Procedure	Outcome
Study physician visit	

 Clinical interview 	
 Bleeding score (ISTH-BAT) RBD bleeding score[52] Children: iCHEC
Questionnaires	

 Self-administered 	
 Demographic characteristics (generic) Socio-economic characteristics (generic) Clinical characteristics (bleeds, treatment), HIV status (patients born before 1985) and hepatitis C status (patients born before 1992) Medical history (generic) Sexuality (generic) General health status (Rand-36/Cho-KLAT) Sports and physical activity (MAQ/HeptestQ) Adherence (VERITAS-pro) Pain (generic) Needle phobia (generic) Experience with care (generic)
Electronic patient records	
	
 Date of birth Sex Baseline factor activity level Baseline factor antigen level Treatment type (prophylactic treatment or on-demand treatment) Body weight and height Bleeding score at diagnosis Relevant previous medical history, i.e. arterial thrombosis, atherosclerosis, medication use, pregnancies and outcomes
Blood samples: 72-83 ml	

 Haemostasis 	
 Screening tests - PFA - Haemoglobin

		
 - Thrombocytes - VWF ristocetin cofactor - VWF antigen - VWF collagen binding assay - FVIII act one stage - FVIII chromogen - aPTT - PT - Fibrinogen - Thrombin time 	
 - Leucocytes & differentiation - Peripheral blood smear - Creatinine - ALAT - TSH - D-dimer - Antitrombin - Protein C - Protein S - TFPI
	
 • Diagnostic tests 	
 - FII - FV - FVII - FIX 	
 - FX - FXI - FXII - FXIII

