6.2. Data collection

Questionnaires

Patients will receive a personal log on code to an electronic questionnaire after informed consent. They will be reminded after one month to fill out the questionnaire online. Patients unwilling or unable to fill out the questionnaire electronically will be provided with a hard copy of the questionnaire. The questionnaires can be found in separate documents. Children’s versions of the questionnaire will be available for children up to 17 years old. Whenever possible, questionnaires specifically validated and designed to be filled out by children will be used. In general, children from 12-17 years old will be able to fill out the questionnaire independently. For children under 12 years old, parents will fill out most of the questions.

The complete questionnaire will take approximately 40-120 minutes to complete, depending on which questions are relevant to the patient. For example, the haemophilia activity list of approximately 50 questions will only be filled out by patients with chronic joint impairment, a

minority in this patient group. The VERITAS-PRO questionnaire will only be performed in patients who are on prophylaxis and patients born after 1992 will not fill out questions about hepatitis C and HIV infections. There are also parts of the questionnaire only for women or certain age-groups. Therefore, we expect that close to no patients will have to fill out all the questions. The questionnaire can be paused at any time and continued later on.

The patients will submit the questionnaires digitally. The questionnaires will be checked and discussed briefly to verify during the patient visit. [The bleeding scores are entered directly into the eCRF.](#)

Blood sampling

All participants will be asked to provide a blood sample during a visit to the haemophilia treatment center. Sampling of 1-5% of an individual's total blood volume is deemed safe according to a systematic review of the literature and of existing guidelines[53]. For this study we will set the maximum around 2.5% of the total blood volume, or 2mL/kg based on a total circulating blood volume of 80mL/kg in persons weighing 2kg or more.

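### Section 8.2 puts the one-week reflection period after informed consent, where it cannot serve its purpose, and the visible text sets no period before signature

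*Combined protocol and SAP*

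**What the plan says.** Section 8.2 (Recruitment and consent) describes recruitment in two steps. First, "Subjects will be informed about the study by their treating physician". Then, "A minimum of one week will be allowed to consider their decision to participate after giving informed consent". It adds that the information letter and consent form are separate documents.

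Three other sections bear on timing:

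- Sections 5.2 and 5.3 make informed consent a condition of entry, with signatories that depend on age. Neither mentions a waiting period.
- Section 6.2 (Questionnaires) makes consent the trigger for access: "Patients will receive a personal log on code to an electronic questionnaire after informed consent". The only other timing there is a reminder: "They will be reminded after one month to fill out the questionnaire online".
- Section 6.1 has the treating physician approach the patient and covers visits or venepunctures that are already scheduled. Of these it says "this can be combined with the study procedures to prevent an extra visit". It gives no minimum interval after information or consent.

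**The concern.** A reflection period protects a patient only if it falls between being informed and committing. Section 8.2 starts the clock once the commitment has been made. A centre that follows the sentence literally could inform the patient, take the signature, and let the week run while the questionnaire is already open. It would comply with the protocol and still not deliver the safeguard that the protocol sets itself.

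What consent opens is not trivial. The questionnaire includes items on sexuality and, depending on year of birth, HIV and hepatitis C status. Sampling from age 12 is roughly 67 mL of blood, of which 20 mL goes to a biobank. Exome sequencing is also planned, with a lower age limit. Around one third of known patients are minors, so parents sign for, or together with, many participants. Section 8.1 makes each local investigator responsible for following the protocol, so the sentence is an operative instruction at eight centres.

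**Working it through.** The plan gives no figure to reproduce. The check sets the stated sequence beside what consent opens.

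**Inputs**

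- Reflection period: at least one week, positioned after consent (Section 8.2).
- Interval between information and signature: not stated in any visible section; call it x days.
- Questionnaire access: triggered by consent, with no delay stated (Section 6.2).
- Reminder: one month (Section 6.2). This prompts late responders and does not set an earliest start.
- Combined visits: allowed, with no minimum interval (Section 6.1).

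**Sequence as written, with consent on day 0**

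1. Day −x: patient informed. Nothing constrains x, so any value from 0 upwards complies.
2. Day 0: consent given.
3. From day 0: questionnaire may be opened.
4. Day 7 at the earliest: reflection period ends.
5. About one month: reminder.

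The questionnaire may be open from day 0 and the minimum reflection period runs from day 0 to day 7, so the permitted overlap is 7 − 0 = 7 days, the whole minimum period. Reflection time guaranteed before signature is the smallest permitted x, which is 0 days. That is a lower bound on what the text guarantees, not an estimate of what patients would get.

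**Sequence with the week before signature**

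1. Day −7 or earlier: information letter received.
2. Day 0: consent given.
3. From day 0: questionnaire and other procedures.

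Guaranteed time before signature is then 7 days, and the overlap with data collection is 0 days.

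**Reach.** The rule applies to all participants. With the 337 known patients in Table 3 and the 70% response expected in Section 5.1, that is 0.70 × 337 = 235.9, about 236 people.

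**Does another section repair it?** Sections 5.2, 5.3 and 6.2 do secure consent before participation and before the log-on code, so that order is sound. They do not secure time before consent. Section 6.3 lets a subject leave at any time without consequences. That is a right exercised after the event, and the section does not say what happens to material already collected.

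**The case against.** The strongest reply is that the meaning is plain despite the wording. The preceding sentence is about being informed, and a week to consider a decision already made is senseless, so the author surely meant a week after receiving the information. The sentence can even be parsed as a week to consider whether to participate, with participation following consent. The information letter and consent form are separate and not available here, and may state the right order. Section 8.1 also binds centres to the Declaration of Helsinki, GCP and Dutch law on research in humans. The study is observational and described as negligible risk.

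Much of this stands. A drafting slip is the likeliest explanation, and the unseen letter may be correct. But the alternative parse is strained, a general reference to GCP does not correct a specific sentence, and if the letter has the right order then protocol and letter disagree and the protocol still needs changing.

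A reader might also infer more than the documents support:

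- **Same-day signature, questionnaire and sampling as the normal course.** Section 6.2 describes an online questionnaire taking 40 to 120 minutes, submitted digitally and then checked at the visit. Saliva collection has conditions reaching back to the evening before. The visit would normally come later. Same-day sampling is not excluded, but it is a worst case.
- **No reflection time for anyone.** The interval before signature is unstated, not zero.
- **Biobank and exome material taken from every child.** The 27 mL draw is for children under 8. They give no biobank blood and fall below both ages that Section 6.2 mentions for exome sequencing (16 and 12).
- **HIV and hepatitis C questions put to everyone.** Table 4 limits them by birth year.
- **Loss of data from a small population.** A patient who decides against taking part contributes nothing under the corrected order either, so the wording does not cause that loss.

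**Conclusion.** The point holds as a minor correction to a rule that is wrong as written. Section 8.2 guarantees at least 7 days after consent and none before it, and Section 6.2 lets the questionnaire open during those 7 days. The rule reaches every participant, about 236 at the expected response.

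This rests on the visible text alone and on reading the sentence in its ordinary sense. It says that early data collection is permitted, not that it will happen. The consequence is confined to participant protection and the soundness of the consent procedure. No sample size, error rate, estimate or analysis depends on it, so it should not be ranked with defects that threaten the study's results.

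**What to change.** Three changes:

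1. Reword Section 8.2 so that subjects, or their parents or guardians where these sign, have at least one week between receiving the information letter and signing informed consent.
2. Check that the separate information letter and consent form give the same order, and align them if they do not.
3. State in Section 6.1 that study procedures may be combined with a planned visit or venepuncture only once that week has passed and consent is signed.

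Section 6.2 can stay as it is: once the week precedes signature, releasing the log-on code on consent no longer overlaps with the time for deciding.

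The cost is a wording change in two sections. Centres that want to use a planned visit must send the letter at least a week ahead, and a patient who first hears of the study at a routine visit cannot be sampled that day.
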